1.5 Interim Analysis

No interim analyses are planned for this study.

2 Analysis Sets

2.1 Efficacy Analysis Sets

All Implanted Analysis Set (AAS):

All subjects with successful IOL implantation in the study eye will be included in the AAS.

The primary analysis set for the primary and exploratory analyses will be the AAS.

Best Case Analysis Set (BAS):

BAS will include the subjects in AAS who had:

- at least 1 postoperative visit,
- no macular degeneration at any time; and
- no major protocol violation

The BAS is a supportive analysis set for the primary and exploratory analyses.

2.2 Safety Analysis Set

All subjects with attempted IOL implantation (successful or aborted after contact with the eye) in the study eye will be considered evaluable and included in the safety analysis set. The safety analysis set will be used for the safety analyses. Additionally, any AE experienced by a subject during the screening period will be presented separately in a listing.

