### 9.3 Exclusion Criteria at Time of Surgery

1. Surgical complications including but not limited to loss of zonular integrity/zonular weakness, zonular rupture, anterior or posterior capsule rupture, any evidence of fluid misdirection during the cataract procedure with progressive shallowing of the anterior chamber, uncontrollable IOP
2. Mechanical or surgical manipulation of the pupil
3. Excessive iris mobility
4. Inability to place the IOL in the capsular bag due to surgical complications

**NOTE:** Subjects who satisfy any of the Exclusion Criteria at the Time of Surgery noted in Section 9.3 will be followed for safety if they are implanted or the IOL touches the eye; and data from these subjects will not be part of the effectiveness data set.

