### **11.8.2 Discontinuations**

Discontinued subjects are individuals who have signed informed consent and who voluntarily withdraw or are withdrawn from the study by the Investigator at the Visit 00/Operative Visit and/or prior to completing all study visits.

Subjects that meet Exclusion Criteria at the time of surgery (refer to Section 9.3) must be captured as discontinuations.

Discontinued subjects will not be replaced; subject numbers of discontinued subjects must not be re-used.

Subjects may discontinue from study at any time for any reason. Subjects may also be discontinued at any time if, in the opinion of the Investigator, continued study participation poses a risk to their health.

If a subject discontinues from the study after Visit 00/Operative Visit, every effort must be made to keep the subject in the study and to continue with the study assessments as specified in the schedule of study procedures and assessments until the final visit.

For subjects discontinuing from the study, the Investigator should complete all Early Exit procedures according to Section 5 Schedule of Study Procedures and Assessments, if the subject is willing and able, and if in the opinion of the Investigator it is safe for the subject to do so.

The Investigator must document the reason for study discontinuation in the subject's case history source documents and complete the exit form in EDC.

To ensure the safety of all subjects who discontinue early, Investigators must assess each subject and, if necessary, advise them of any therapies and/or medical procedures that may be needed to maintain their health.

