### **12.4.5 Device Deficiencies**

A device deficiency is an inadequacy of a medical device with respect to its identity, quality, durability, reliability, safety, or performance. This definition includes malfunctions, use errors, and inadequate labeling. Malfunction is defined as a failure of a medical device to perform in accordance with its intended purpose when used in accordance with the instructions for use or clinical investigation plan. Use error is defined as an act or omission of an act that results in a different medical device response than intended by manufacturer or expected by user; this includes slips, lapses, and mistakes. An unexpected physiological response of the subject does not in itself constitute a use error.

A device deficiency may or may not be associated with subject harm (ie, ADE or SADE); however, not all ADEs or SADEs are due to a device deficiency. The Investigator must determine the applicable category for the identified or suspect device deficiency and report any subject harm separately. Examples of device deficiencies include the following:

- Failure to meet product specifications (eg, incorrect IOL power,)
- IOL defect
- Broken IOL optic
- Broken IOL haptic
- Scratched IOL optic
- Unsealed device packaging
- Lack of efficacy
- Autorefractor errors and other diagnostic equipment related deficiencies

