### **13.2 Analysis Data Sets**

#### **13.2.1 Safety Analysis Set**

All subjects with attempted IOL implantation (successful or aborted after contact with the eye) in at least one eye will be considered evaluable and included in the safety analysis set. The safety analysis set will be used for the safety analyses. Additionally, any AE experienced by a subject during the screening period will be presented separately in the safety analysis.

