5.3 Statistical Methods for Safety Analyses

Except otherwise stated, the analysis set for all safety analyses is the safety analysis set as defined in Section 2.2. Baseline will be defined as the last measurement prior to exposure to investigational product, except otherwise stated.

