5.3.3 Surgical Problems

The number and percentage of eyes with surgical problems will be presented. In addition, a listing of subjects with surgical problems will be provided. The listing will include the following variables: investigator, subject, age, sex, race, ethnicity, eye and description of surgical problem.

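### The safety set requires lens contact, so an eye whose surgical complication ended the procedure with no study-lens contact is left out of the surgical-problem table, and that rate is low for operated eyes.

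*SAP*

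**What the plan says.** SAP 2.2 admits a subject to the safety set on this rule: "All subjects with attempted IOL implantation (successful or aborted after contact with the eye) in the study eye will be considered evaluable". Protocol 13.2.1 has the same contact condition, though it refers to a different eye: "All subjects with attempted IOL implantation (successful or aborted after contact with the eye) in at least one eye will be considered evaluable". Only one eye per subject is enrolled, so that difference does not affect this point, but the two texts should agree.

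SAP 5.3 then states, subject only to exceptions given elsewhere, that "the analysis set for all safety analyses is the safety analysis set as defined in Section 2.2". SAP 5.3.3 gives no exception: "The number and percentage of eyes with surgical problems will be presented". Surgical problems are a named safety assessment in Protocol 7.3.2 and 13.7 and in SAP 5.1.

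Protocol 9.3 lists complications such as zonular or capsular rupture as exclusions at the time of surgery, together with "Inability to place the IOL in the capsular bag due to surgical complications". Subjects who meet these criteria "will be followed for safety if they are implanted or the IOL touches the eye". On disposition, Protocol 11.8.2 says: "Subjects that meet Exclusion Criteria at the time of surgery (refer to Section 9.3) must be captured as discontinuations". They are not screen failures, because Protocol 11.8.1 keeps that label for subjects who leave before the operative visit. Protocol 11.2 has surgical problems, AEs and device deficiencies recorded at Visit 00, whether or not the lens touched the eye.

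The only AEs for which either document provides a presentation outside the safety set are those of the screening period (SAP 2.2, Protocol 13.2.1).

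**The concern.** Membership of the safety set depends in part on the outcome that SAP 5.3.3 is meant to count. If a complication stops the operation before any study lens makes contact, the subject has had study surgery and the problem is on the case report form. The subject nevertheless enters neither the count nor the denominator. The complications removed are those serious enough to prevent implantation, so the remaining rate describes only eyes that reached lens contact.

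A second gap concerns AEs. An AE that begins at Visit 00 in such an eye is not a screening-period AE, and the subject is not in the safety set, so the SAP assigns it no table.

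What is at stake is the accuracy of one descriptive rate and the completeness of AE reporting for a small group. The equivalence analysis is not affected.

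**Working it through.** **Inputs.** Protocol 9 plans 183 subjects enrolled, 165 eligible and 144 completing. These agree with its stated rates to within rounding: 183 × 0.90 = 164.7 and 165 × 0.87 = 143.55. I take 165 as the number of operated eyes, because subjects who leave before the operative visit count as screen failures. Neither document gives a rate for surgical problems, AEs or aborted implantations, so the values below are assumptions:

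- N = 165 operated eyes
- k = operated eyes dropped because no study lens touched them, taken as 1, 3 or 5
- x = retained eyes with the event, taken as 2, 5 or 8
- j = dropped eyes with the event

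**Formula.** The plan reports x/(N − k). The rate among all operated eyes is (x + j)/N. The reported rate is the lower of the two only if j/k exceeds x/(N − k).

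**Surgical problems.** Each eye dropped because of a complication has the event, so j = k. The shortfall is then

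(x + k)/N − x/(N − k) = (k/N) × [1 − x/(N − k)],

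which is positive unless every retained eye has a problem.

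| x | k | Reported | All operated | Shortfall (points) |
|---|---|---|---|---|
| 2 | 1 | 2/164 = 1.22% | 3/165 = 1.82% | 0.60 |
| 2 | 3 | 2/162 = 1.23% | 5/165 = 3.03% | 1.80 |
| 2 | 5 | 2/160 = 1.25% | 7/165 = 4.24% | 2.99 |
| 5 | 1 | 5/164 = 3.05% | 6/165 = 3.64% | 0.59 |
| 5 | 3 | 5/162 = 3.09% | 8/165 = 4.85% | 1.76 |
| 5 | 5 | 5/160 = 3.12% | 10/165 = 6.06% | 2.94 |
| 8 | 1 | 8/164 = 4.88% | 9/165 = 5.45% | 0.58 |
| 8 | 3 | 8/162 = 4.94% | 11/165 = 6.67% | 1.73 |
| 8 | 5 | 8/160 = 5.00% | 13/165 = 7.88% | 2.88 |

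The shortfall is about 0.6 point per dropped eye and depends little on x.

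**AEs.** A surgical problem need not be recorded as an AE, so j can be anything from 0 to k. With x = 5 and k = 3 the reported rate is 5/162 = 3.09%. Among all operated eyes it would be 5/165 = 3.03% if j = 0, 6/165 = 3.64% if j = 1, and 8/165 = 4.85% if j = 3. The reported rate is slightly high in the first case and low in the other two.

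**Device deficiencies.** A purely surgical failure is not a deficiency, so j = 0. With x = 5 the rate among all operated eyes is 5/165 = 3.03%, and the reported rate is 3.05% to 3.12% for k = 1 to 5. Dropping such eyes raises this rate slightly.

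**The case against.** A reader might infer that the surgical-problem, AE and device-deficiency rates are all biased low. The documents do not support that.

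- **Device deficiencies.** A complication before contact removes only a denominator eye. A defect found before contact, such as "Unsealed device packaging" in Protocol 12.4.5, does not by itself lose the eye: Protocol 11.10.1 permits a second attempt, and discontinuation is required only after a second abort with no contact on either attempt (11.10.2). SAP 5.3.2 also tabulates and lists all deficiencies, which can be read as an exception to the default set.
- **AEs.** The direction depends on j, as shown above. The safety objective in Protocol 7.3 concerns AE rates for the lens and for use of the autorefractor. A set of exposed eyes suits that objective, so there is no case for moving the main AE tables to a wider set.
- **Which eyes are lost.** Rupture before the lens is introduced does not in itself exclude an eye. If the lens is later implanted or touches the eye, the eye stays in the safety set. Only eyes with no study-lens contact at all are lost.
- **Visibility.** SAP 3 plans a disposition table and a listing of subjects excluded from key analysis sets, with reasons, and SAP 5.3.1 displays AE information by subject. The exclusions are not hidden.

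All four points stand as limits on the concern. They do not answer it for surgical problems. The listing in SAP 3 may show that an eye was excluded, but it does not restore that eye to the rate in SAP 5.3.3. The by-subject AE display falls under the same default set in SAP 5.3. An objective framed around the lens gives no reason to make surgical problems conditional on lens contact.

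**Conclusion.** The point holds for the surgical-problem table. Under SAP 2.2, 5.3 and 5.3.3, eyes in which a complication ended the procedure with no study-lens contact are left out because of the event being counted, so the rate is low for operated eyes. The shortfall is about 0.6 percentage point per such eye out of 165, or about 0.6 to 3.0 points for one to five eyes. This takes all 165 eligible subjects as operated and each dropped eye as having a recorded surgical problem. The true number of such eyes is unknown and may be zero, in which case nothing changes.

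For intraoperative AEs the finding is a reporting gap: an AE at Visit 00 in a no-contact eye has no assigned table. The effect on the AE rate can go either way. It would be wrong to read the rule as favourable for every safety rate, or as lowering the device-deficiency rate.

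SAP 5.2 states that there are no formal safety hypotheses, so no success criterion depends on this. It is an inexpensive correction to a descriptive table.

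**What to change.** 1. In SAP 5.3.3 and Protocol 13.7, state that surgical problems are counted among all subjects in whom study-eye surgery was started, in both numerator and denominator, whether or not a study lens touched the eye. Define the start of surgery.
2. In SAP 5.3.1, add a separate listing or table of AEs with onset at Visit 00 in eyes with no lens contact.
3. Keep the contact-based safety set for the main AE tables and for the lens-specific endpoints: IOL observations, IOL position change, posterior capsule opacification and capsulotomy.

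The cost is one extra population flag and a few sentences in each document. Protocol 11.2 already has the data recorded at Visit 00. The surgical-problem rate may come out less favourable.

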2.3 Pharmacokinetic Analysis Set

Not Applicable.

3 Subject Characteristics and Study Conduct Summaries

Subject characteristics and study conduct summaries include tables and listings such as a subject disposition table, demographics and baseline characteristics tables (including age, gender, race, and ethnicity, summary of screen failures by reason and listing of subjects excluded from key analysis sets including reasons.

All descriptive summary statistics will be displayed with n and % for categorical data, and with mean, median, standard deviation, number of subjects, minimum, and maximum for continuous data.

[figure not shown]
Subject characteristics and study conduct summaries will be presented for the AAS (Overall and by site) and safety set (overall only). Subject characteristics and study conduct summaries for the BAS (overall and by site) will be presented if the total number of subjects excluded exceeds 10%.

4 Effectiveness Analysis Strategy

4.1 Efficacy Endpoints

The primary [REDACTED] endpoints are:

- IOL SRK/T A-constant estimated based on the preoperative biometry, IOL power and postoperative manifest spherical equivalent refraction at 3 months and
- IOL SRK/T A-constant estimated based on the preoperative biometry, IOL power and postoperative spherical equivalent from autorefractometry using *Topcon KR-1W* at 3 months.

4.2 Efficacy Hypotheses

[figure not shown]
4.2.1 Primary Effectiveness Hypothesis

[figure not shown]
The null and alternative hypotheses for the primary analysis are:

$$H_0: \mu_{diff} \leq -0.15 \text{ or } \mu_{diff} \geq 0.15$$

$$H_A: -0.15 < \mu_{diff} < 0.15$$

Where μ_{diff} refers to the mean paired difference between the first two endpoints listed in section 4.1 for each site.

4.3 Statistical Methods for Efficacy Analyses

The primary hypothesis will be tested by generating a 2-sided 90% confidence interval for the paired difference at each site. Equivalence will be declared if the bounds of the 90% CI are contained within the equivalence range (-0.15, 0.15). SAS PROC TTEST will be used to generate the confidence interval based on the pseudo code below:

```
proc ttest data=Aconst alpha=0.1;  
  paired AconstMR*AconstAR;  
run;
```

Additionally, as a sensitivity analysis, a mixed effects model will be fit to estimate overall effect of refraction method as well as by site. The pseudo code is provided below:

```
proc mixed data=Aconst;  
  class subj RefMethod Site;  
  model SBP=RefMethod|site;  
  repeated RefMethod / subject=subj type=un;  
  lsmeans RefMethod*site/diffs cl ;  
run;
```

Descriptive statistics (mean, median, standard deviation, number of eyes, minimum, maximum, and two-sided 90% confidence interval) will be provided for each site for the A-constants calculated using manifest refraction and autorefraction and also for the difference.

[figure not shown]
Alcon - Business Use Only

Effective Date: 01-Sep-2016

Document: TDOC-0052874

Version: 2.0; CURRENT; Most-Recent; Effective

Status: Effective

Printed By:

Print Date:

[figure not shown]
Alcon - Business Use Only

Effective Date: 01-Sep-2016

Document: TDOC-0052874

Version: 2.0; CURRENT; Most-Recent; Effective

Status: Effective

Printed By:

Print Date:

4.4 Multiplicity Strategy

No multiplicity adjustments are planned for primary or exploratory analyses. The primary hypothesis tests must be rejected at every site for the study to be considered a success.

4.5 Interim Analysis for Efficacy

No interim analysis is planned.

5 Safety Analysis Strategy

5.1 Safety Endpoints

The safety assessments are:

- Adverse events (AEs) including secondary surgical intervention (SSI)
- Device deficiencies (DD)
- Surgical problems
- Intraocular pressure (IOP)
- Slit lamp examination
- IOL observations
- IOL position change
- Subjective posterior capsule opacification (PCO)
- Posterior capsulotomy
- Dilated fundus examination

5.2 Safety Hypotheses

There are no formal safety hypotheses in this study. The focus of the safety analysis will be a comprehensive descriptive assessment of safety endpoints listed in Section 5.1.

5.3 Statistical Methods for Safety Analyses

Except otherwise stated, the analysis set for all safety analyses is the safety analysis set as defined in Section 2.2. Baseline will be defined as the last measurement prior to exposure to investigational product, except otherwise stated.

5.3.1 Adverse Events

All information obtained on AEs will be displayed by subject.

The number and percentage of all ocular adverse events, including secondary surgical interventions (SSIs), will be tabulated by preferred term. An eye with multiple ocular AEs of the same preferred term is only counted once toward the total of this preferred term.

The number and percentage of all adverse events will also be tabulated.

Adverse events will be summarized in the following tables:

- All Adverse Events (Serious and Non-Serious Combined)
 - Ocular
 - Non-Ocular
- All Adverse Device Effects
 - Ocular
 - Non-Ocular
- All Serious Adverse Events (including Serious Adverse Device Effects)
 - Ocular
 - Non-Ocular
- Subject Listings
 - Non-Serious Ocular
 - Non-Serious Non-Ocular
 - Serious Ocular
 - Serious Non-Ocular

5.3.2 Device Deficiencies

The number and percentage of all device deficiencies will be tabulated. A listing of all device deficiencies, as recorded on the Device Deficiency Form, will also be provided.

5.3.3 Surgical Problems

The number and percentage of eyes with surgical problems will be presented. In addition, a listing of subjects with surgical problems will be provided. The listing will include the following variables: investigator, subject, age, sex, race, ethnicity, eye and description of surgical problem.

5.3.4 Intraocular Pressure

Intraocular pressure (IOP) measurements will be recorded in mmHg and rounded to the nearest whole mmHg. Descriptive summaries (N, mean, median, standard deviation, standard error, minimum and maximum) of observed values and change from baseline values will be presented at each study visit. A listing will be provided which presents all eyes with an increase or decrease in IOP of more than 10 mmHg at any visit compared to the same eye at baseline. The listing will include the following variables: investigator, subject, age, sex, race, ethnicity, visit, eye, baseline value, value at the visit and a change from baseline value.

5.3.5 Slit Lamp Examination

For each slit-lamp parameter, number and percentages of eyes that experience abnormality at any post-operative visit will be presented. A listing will be provided which presents all eyes with an abnormality in any slit-lamp parameter at any post-operative visit. The listing will include all slit-lamp data from all visits with the following variables: investigator, subject, age, sex, race, ethnicity, visit, eye, parameter, baseline value, and value at the visit.

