## 9.2 Exclusion Criteria

Subjects fulfilling **any** of the following criteria are not eligible for inclusion in this study:

1. Women of childbearing potential, defined as all women who are physiologically capable of becoming pregnant and who are not postmenopausal for at least 1 year or are less than 6 weeks since sterilization, are excluded from participation if any of the following apply:
  - a. they are currently pregnant
  - b. have a positive urine pregnancy test result at Screening/Visit 0
  - c. intend to become pregnant during the study period
  - d. are breast-feeding

2. History of any condition with associated fluctuation of hormones that could lead to refractive changes
3. History of anterior segment (corneal, anterior chamber, sulcus) or posterior segment (uveal, vitreo-retinal) pathology including retinal vascular occlusive disease, retinal detachment or peripheral retinal laser photocoagulation, age-related macular degeneration (AMD), glaucoma, diabetic retinopathy, retinitis pigmentosa and any optic nerve pathology
4. History of recurrent anterior segment /posterior segment inflammation
5. Clinically significant, in the opinion of the Investigator, any corneal dystrophy or any other corneal abnormality/pathology (epithelial, stromal or endothelial) including but not limited to the following: keratitis, keratoconjunctivitis and keratouveitis
6. Clinically significant, in the opinion of the Investigator, severe dry eye
7. History of previous intraocular or corneal surgery
8. Diagnosis of amblyopia
9. Systemic medications that, in the opinion of the Investigator, may confound the outcome or increase the risk of complications to the subject (eg, Tamusolin Hydrochloride – Flomax) or other medications including anticholinergics, alpha adrenergic blocking agents with similar side effects (eg, small pupil/floppy iris syndrome)
10. Concurrent participation in another clinical study that, in the Investigator’s opinion, may confound the results of the current study
11. Any other ocular or systemic co-morbidity that, in the opinion of the Investigator, may confound the results of this study or prohibit the completion of the study assessments or increase the risk for the subject
12. Subjects with conditions that increase the risk of zonular rupture during cataract extraction procedure that may affect the postoperative centration or tilt of the lens

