## **12.7 Procedures for Recording and Reporting**

All AEs must be documented on the AE electronic case report form (eCRF) by the site and are monitored on a routine basis by the Study Sponsor.

AEs are collected from the time of informed consent. Any pre-existing medical conditions or symptoms present in a subject are not considered AEs in the study. Aqueous cells and flare, corneal edema, raised IOP and superficial punctate keratitis are examples of early postoperative findings that are typically observed following ocular surgery. These are not considered AEs if they can be reasonably expected to resolve within a week and not result in any untoward long term visual outcome impact.

The Investigator must promptly document all ADEs and SAEs with details including the date of occurrence, severity, treatment (if applicable), outcome, and assessments of the seriousness and causality. In addition, the Investigator must promptly document all device deficiencies on the *Device Deficiency* eCRF. The site must submit all available information on ADEs, SAEs, and device deficiencies to the Study Sponsor immediately as follows:

- **ADEs or SAEs are documented on the *Adverse Device Effect and Serious Adverse Event* eCRF within 24 hours of the Investigator's or site's awareness.**
- **Device deficiencies are documented on the *Device Deficiency* eCRF within 24 hours of the Investigator's or site's awareness. Please include a printed copy of the completed *Device Deficiency* eCRF with product returns.**
- **Additional relevant information after initial reporting is to be entered into the eCRF as soon as the data become available.**
- **Document any changes to concomitant medications on the appropriate eCRFs.**
- **All relevant documentation such as Discharge Summary, Autopsy Report, Certificate of Death etc, must be faxed to the Study Sponsor at [REDACTED]**

**NOTE:** Should the EDC system become non-operational, the site must complete the appropriate paper *Adverse Device Effect and Serious Adverse Event Form* or *Device Deficiency Form*. The completed form is faxed to the Study Sponsor at [REDACTED] within 24 hours of the Investigator's or site's awareness; however, the reported information must be entered into the EDC system once it becomes operational.

**Sponsor representatives and their contact information are provided in the Manual of Procedures that accompanies this protocol.**

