5.3.10 Dilated Fundus Examination

For each dilated fundus parameter, number and percentages of eyes that experience abnormality at any post-operative visit will be presented. A listing will be provided which presents all eyes with abnormality in any fundus parameter at any post-operative visit. The listing will include the following variables: investigator, subject, age, sex, race, ethnicity, visit, eye, baseline value and value at the visit.

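### The slit-lamp and fundus safety tables report postoperative prevalence without reference to baseline, so they cannot separate stable pre-existing findings from new or worsened ones

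*SAP*

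**What the plan says.** SAP 5.3.5 states: "For each slit-lamp parameter, number and percentages of eyes that experience abnormality at any post-operative visit will be presented". SAP 5.3.10 repeats the rule for the other examination: "For each dilated fundus parameter, number and percentages of eyes that experience abnormality at any post-operative visit will be presented". Protocol 13.7 asks only for counts and percentages per category for categorical safety data and adds no baseline condition.

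A baseline is available. The schedule in Protocol section 5 and the steps in 11.1 place both examinations at Visit 0. SAP 5.3 says: "Baseline will be defined as the last measurement prior to exposure to investigational product, except otherwise stated".

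The baseline is used elsewhere. For intraocular pressure, SAP 5.3.4 says that "observed values and change from baseline values will be presented at each study visit". The listings that accompany the two tables also carry it. For the slit lamp, "The listing will include all slit-lamp data from all visits with the following variables" introduces a set of variables that includes the baseline value. The fundus listing ends with "visit, eye, baseline value and value at the visit".

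**The concern.** As the two rules are written, an eye with the same abnormality before and after surgery enters the numerator in the same way as an eye whose abnormality first appears after surgery. Every subject receives the same lens (SAP 1.3), so there is no second arm from which to read the background. SAP 5.2 makes the descriptive assessment the whole of the safety analysis. A reader of these two tables would want to know what changed after implantation, and the percentages do not show it.

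Eyes with mild pre-existing findings can enter the study. Among the exclusions in Protocol 9.2 is "Clinically significant, in the opinion of the Investigator, severe dry eye", and corneal abnormality in exclusion 5 is likewise qualified by clinical significance in the Investigator's judgement. Milder findings of these kinds are not barred by those two criteria.

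**Working it through.** The documents state no rate for these tables, so there is no figure to reproduce. The check has two parts.

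**1. Text, side by side**

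| Item | Examined before surgery? | Tabulated summary uses baseline? | Listing shows baseline? |
|---|---|---|---|
| Intraocular pressure (SAP 5.3.4) | Yes | Yes, change from baseline | Yes |
| Slit lamp (SAP 5.3.5) | Yes | No | Yes |
| Dilated fundus (SAP 5.3.10) | Yes | No | Yes |

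That the two tables ignore baseline is inferred from the absence of any baseline condition; the SAP does not say so in words. The verb in both rules could be meant as new onset, but nothing in SAP 5.3, 5.3.5, 5.3.10 or Protocol 13.7 defines it that way.

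**2. Illustration of size (all rates assumed)**

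Let b be the share of eyes with a stable abnormality on one parameter at baseline, and i the share of the remaining eyes that develop a new one. Worsening of an existing abnormality is ignored.

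- Share counted by the current rule: b + (1 − b)i
- Share with a new abnormality: (1 − b)i
- Pre-existing part of the count: b / [b + (1 − b)i]

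Low end, b = 1% and i = 3%: 0.01 + 0.99 × 0.03 = 0.0397. The new share is 0.0297 and the pre-existing part is 0.01 / 0.0397 = 25%. The ratio of tabulated to new is 0.0397 / 0.0297 = 1.3.

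High end, b = 20% and i = 1%: 0.20 + 0.80 × 0.01 = 0.208. The new share is 0.008 and the pre-existing part is 0.20 / 0.208 = 96%.

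The full grid, with eye counts for the planned minimum of 165 subjects (one eye each):

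| b | i | Counted by current rule | New only | Pre-existing part |
|---|---|---|---|---|
| 1% | 1% | 3.3 eyes (2.0%) | 1.6 | 50% |
| 1% | 3% | 6.6 (4.0%) | 4.9 | 25% |
| 5% | 1% | 9.8 (6.0%) | 1.6 | 84% |
| 5% | 3% | 13.0 (7.8%) | 4.7 | 64% |
| 10% | 1% | 18.0 (10.9%) | 1.5 | 92% |
| 10% | 3% | 21.0 (12.7%) | 4.5 | 79% |
| 20% | 1% | 34.3 (20.8%) | 1.3 | 96% |
| 20% | 3% | 37.0 (22.4%) | 4.0 | 89% |

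The percentages do not depend on the number of eyes. The tables are per parameter, so b is the baseline rate of a single finding among eligible eyes.

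**The case against.** A good deal can be said for leaving the tables alone, and most of it stands.

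- **New clinical problems are captured elsewhere.** Protocol 12.6 has the Investigator review changes in protocol-specific ocular parameters and report any clinically relevant untoward change as an adverse event, whatever its cause. SAP 5.3.1 tabulates ocular adverse events by preferred term. Protocol 12.7 keeps the background out of those tables: "Any pre-existing medical conditions or symptoms present in a subject are not considered AEs in the study". A reader might infer that a real safety signal would be hidden. The documents do not support that; what stays untabulated is change judged not clinically relevant.
- **The tables are not wrong as labelled.** An eye abnormal before and after surgery is abnormal after surgery, and the SAP never calls these counts new or device-related. A reader might infer that the tables overstate postoperative abnormality. They do not: they report prevalence, which is less informative here than incidence.
- **The listings separate the two.** Both cover every eye with a postoperative abnormality and show its baseline value, so stable and new findings can be told apart eye by eye. That information is missing only from the summary percentages.
- **Eligibility is stricter than exclusions 5 and 6 suggest.** Exclusion 3 removes a history of anterior or posterior segment pathology, with no clinical-significance qualifier. For the fundus table in particular, the corneal and dry-eye thresholds offer no route of entry, so the case is weaker there.
- **Grading is not established.** Assessment detail is left to the Manual of Procedures. Neither document lists the parameters, defines abnormality or says that findings are graded.
- **Before and after are not always comparable.** The baseline eye has a cataract and the postoperative eye has an implant. Lens items change by design, and a fundus finding hidden by the cataract could look new.

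These arguments limit the consequence and shape the remedy. They do not give the two percentages a baseline reference.

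**Conclusion.** The point holds as a minor matter of safety reporting. The tables in SAP 5.3.5 and 5.3.10 give postoperative prevalence, and in a single-arm study those percentages alone cannot distinguish stable pre-existing findings from new or worsened ones. The adverse event tables are unaffected, there is no safety hypothesis, and study success depends only on A-constant equivalence.

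The size is unknown. The 25% to 96% range rests wholly on assumed baseline rates of 1% to 20% and new rates of 1% to 3%, and exclusion 3 may hold actual baseline rates near or below the low end. A reader might infer a several-fold inflation of the abnormality rate. The documents do not support any particular multiple: at 1% baseline and 3% new the ratio is only about 1.3, and larger values follow from the inputs one chooses.

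**What to change.** In SAP 5.3.5 and 5.3.10, add for each parameter the number and percentage of eyes with a postoperative abnormality that was absent at the SAP 5.3 baseline, or that worsened where the parameter is graded. The denominator should be eyes with a baseline and at least one postoperative examination of that parameter. A table of baseline status against worst postoperative status would serve equally well.

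Keep the present count alongside. Flag parameters that cannot be compared across cataract removal, such as lens items and fundus views obscured by cataract at baseline, so that they are not read as new events.

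The cost is SAP wording, one derived flag from data already collected and one extra column. Study conduct does not change. The only care needed is with the non-comparable parameters.
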